### 7.7 Safety analysis

This section describes the safety analyses that will be conducted including all data collected in subjects who drop out.

All definitions relative to safety endpoints are detailed in [Section 3](#).

Safety analyses will be conducted on the safety population and will be performed for all safety variables specified below. All safety data will be summarized by treatment group. The summaries/analyses will be stratified according to NP positive/negative status of the subjects, prior receipt of any non-study prophylactic COVID-19 vaccine of the subjects, and age group. Strata for age group are 18 – 50, 51+ and 65+ years at Dose 1. Strata for NP status are positive and negative at each time point. Strata for prior receipt of any non-study prophylactic COVID-19 vaccine are yes and no at each time point. Additionally, a composite stratification of NP positive or non-study vaccinated and NP negative and not non-study vaccinated will be utilized.

The safety analyses of changes from baseline to a specific time point in safety variables (e.g., laboratory parameters, vital signs, ECG) will include subjects from the safety population who have data available for both the baseline and the time point under considerations unless otherwise specified.

#### 7.7.1 Adverse events

All adverse events (AE) will be classified by Primary System Organ Class (SOC) and Preferred Term (PT) according to the Medical Dictionary for Regulatory Activities (MedDRA) Version 23.0 or higher.

In summaries by SOC and PT, adverse events will be sorted by descending frequency within each SOC and PT according to the total number of events. In summaries by PT, AEs will be sorted by decreasing frequency according to the total number of events.

All AEs will be captured from the time of the informed consent until 28 days post-dose 2 (Day 56). Following the Day 56 visit, only SAEs, AESIs and MAAEs will be collected.

## Statistical Analysis Plan (SAP) - Phase 2 Segment

---

AEs will be classified as pre-treatment or treatment emergent (TEAE) defined as follows:

- Pre-treatment: any AE that started before the first dose date of the study treatment
- TEAE: any AE that was newly developed at or after the first dose date of study treatment

Details for imputing missing or partial start dates of adverse events are described in [section 6.2](#).

AE summary tables will include the following:

- All TEAEs
- Related TEAEs (AE will be defined as related if causality is either probable, possible, or definite)
- TEAEs by maximum severity
- TEAEs leading to treatment discontinuation
- Serious TEAEs
- TEAEs leading to death

All AEs including injection-site reactions will be summarized among the Safety Population by frequency per treatment arm. These frequencies will be presented overall and separately by dose, and will depict overall, by system organ class and by preferred term, the percentage of subjects affected.

Where a subject has the same adverse event, based on preferred terminology, reported multiple times in the treatment period, the subject will only be counted once at the preferred terminology level in adverse event frequency tables.

Where a subject has multiple adverse events within the same system organ class in the treatment period, the subject will only be counted once at the system organ class level in adverse event frequency tables.

Adverse events by severity and separately by relationship will be summarized based on the most intense event during the treatment period and strongest relationship to study treatment, respectively.

The main summary of safety data will be based on events occurring within 30 days of any dose. For this summary, the frequency of preferred term events will be compared between study arms with risk differences and 95% confidence intervals, using the method of Miettinen and Nurminen. As this analysis will use many event categories, and produce many confidence intervals, caution should be exercised when interpreting these confidence intervals. Separate summaries will be based on events occurring within 7 days of any dose and regardless of when they occurred.

The following sample of SAS code will be used to construct confidence intervals of the risk difference with the method of Miettinen and Nurminen:

```
proc freq data = <DATASET>;
  tables armcd * <OUTCOME> / riskdiff(CL= MN);
```

---

```
weight <COUNT>;  
run;
```

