## Statistical Analysis Plan (SAP) - Phase 2 Segment

Table 2: Phase 2 Segment Schedule of Events

Tests and assessments	Sc	D0		Tel #1	Wk 4		Tel #2	Wk6	Tel #3	Wk 30	Wk 56	Illness	Illness	
	Screen a	Pre	Post	Day 0	Pre	Day 28 (±3d)	Post	Day 35 (±3d)	Day 42 (±5d)	Phone Call - Day 56 (±5d)	Day 210 (±5d)	Day 393 (± 5d)	COVID-19 assessment visit m	COVID-19 convalescent visit n
Informed Consent	X													
Inclusion/Exclusion Criteria	X													
Medical history	X	X												
Demographics	X													
Socio-behavioral Assessment	X													
Concomitant Medications	X	X		X	X		X	X	X	X	X	X	X	X
Physical Exam b	X	X			X			X		X	X	X	X	X
Vital Signs	X	X			X			X		X	X	X p	X p	X p
Height and Weight	X													
CBC with differential f	X	X			X			X				X		
Chemistry c	X	X			X			X				X		
HIV Serology		X												
Urinalysis Routine d	X	X			X			X				X		
Pregnancy Test e	X	X			X							X		
INO-4800 or Placebo + EP f		X			X									
Download EP Data g			X			X								
Adverse Events h	X	X	X	X	X	X	X	X	X	X	X	X	X	X
Cellular Samples i		X						X		X	X			X
Humoral Samples j		X						X		X	X			X
SARS-CoV-2 Serology k	X													
SARS-CoV-2 RT-PCR (Saliva and Swab)	X l											X l	X l	
Distribute Diary			X			X								
Review/Collect Diary o				X	X		X	X						

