#### 7.5.2 Treatment compliance

A full course of study product administration consists of two doses of vaccine. A summary table detailing the total number of doses received will be presented along with the reason a dose was not administered or missed. A summary of subjects receiving the dose outside the dosing window, 25 to 31 days post first dose, will be presented.

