#### 5.4.1 Adverse Events and Deaths

All AEs will be classified by Primary System Organ Class (SOC) and Preferred Term (PT) according to the Medical Dictionary for Regulatory Activities (MedDRA) Version 23.0 or higher.

In summaries by SOC and PT, AEs will be sorted by descending frequency within each SOC and PT according to the total number of events. In summaries by PT, AEs will be sorted by descending frequency according to the total number of events.

AEs will be classified as pre-treatment or treatment emergent (TEAE) defined as follows:

- Pre-treatment: any AE that started before the first dose date of the study treatment
- TEAE: Any AE that was newly developed at or after the first dose date of study treatment.

Details for imputing missing or partial start dates of AEs are described in SAP section [3.5.2.1](#).

AE summaries will include the following:

- All TEAEs
- Related TEAEs (AE will be defined as related if causality is either probably, possible, or definite)
- TEAEs by maximum severity, including grade  $\geq 3$
- Medically Attended AEs
- TEAEs leading to treatment discontinuation
- Serious TEAEs
- TEAEs leading to death

All AEs, including injection-site reactions, will be summarized among the Safety Population by frequency per treatment arm. These frequencies will be presented overall and separately by dose, and will depict overall, by system organ class and by preferred term, the percentage of subjects affected. In addition, an overall summary for categories above will be prepared by treatment arm.

Where a subject has the same AE, based on preferred terminology, reported multiple times in the treatment period, the subject will only be counted once at the preferred terminology level in AE frequency.

Where a subject has multiple AEs within the same system organ class in the treatment period, the subject will only be counted once at the system organ class level in AE frequency.

Adverse events by severity and separately by relationship will be summarized based on the most intense event during the treatment period and strongest relationship to study treatment, respectively.

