## Statistical Analysis Plan (SAP) – Phase 3 Segment

- d. Intradermal injection(s) in skin preferably over deltoid region, or alternately over anterolateral quadriceps region, followed by EP at Day 0 and Day 28.
- e. Following administration of INO-4800 or placebo, EP data will be downloaded from the CELLECTRA® 2000 device and provided to Inovio.
- f. AEs to be collected from time of consent to Day 56; SAEs, MAAEs, and AESIs to be collected from time of consent to EOS.
- g. On Day 0, cellular sampling requires 64 mL of whole blood prior to 1st dose. At all other time points, collect 32 mL of whole blood. Cellular samples will be collected at selected clinical sites (estimated to include 711 subjects).
- h. On Day 0, humoral sampling requires a total of 17 mL of whole blood (two 10-mL red top serum collection tubes, each 8.5 mL of whole blood, to produce four serum aliquots of 2 mL each). At all other time points, collect 8.5 mL of whole blood in a single 10-mL red top serum collection tube to produce two serum aliquots of 2 mL each.
- i. SARS-CoV-2 antibody.
- j. The Day 0 RT-PCR results will not be required prior to dosing on that day.
- k. Day 42 visit must occur at least 10 days after Day 28 visit.
- l. Subjects will be evaluated during a "COVID-19 assessment visit" when acute COVID-19 is suspected. The assessment visit may be performed in the clinic, subject's vehicle, or at a home visit and should be completed within 3 days of symptom onset or within 3 days of a positive result of a SARS-CoV-2 test.
- m. For subjects with confirmed SARS-CoV-2 infection during the trial, a convalescent visit should be scheduled approximately 28 days after symptom onset, or in the absence of symptoms, the date of positive SARS-CoV-2 test. If acute symptoms are ongoing the site should follow up with the subject via phone call or unscheduled visit after symptom resolution or stabilization.
- n. Vital signs to be performed at COVID-19 assessment and convalescent visits include temperature, respiration rate, heart rate and oxygen saturation.
- o. Genotyping may also be performed on sample(s) collected at the COVID-19 assessment visit.
- p. Diaries to be used at selected sites only (estimated to include 711 subjects).
- q. Diary should be reviewed at the 14-day post-dose phone call or visit and collected at the next in-office visit.

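### The main safety summary covers 30 days after any dose, but ordinary adverse events are collected only to 28 days after Dose 2 (Day 56)

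*SAP*

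**What the plan says.** **Analysis window.** Phase 2 SAP, section 7.7.1: "The main summary of safety data will be based on events occurring within 30 days of any dose". Phase 3 SAP, section 5.4.1, repeats the sentence. In both, this summary compares preferred-term frequencies between arms by Miettinen-Nurminen risk differences. Separate summaries cover 7 days after any dose and all events whenever they occurred.

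**Collection.** The same Phase 2 section says: "All AEs will be captured from the time of the informed consent until 28 days post-dose 2 (Day 56"), and then: "Following the Day 56 visit, only SAEs, AESIs and MAAEs will be collected". Footnote h of the Phase 2 schedule (Table 2) agrees. Footnote f of Phase 3 Appendix A says: "AEs to be collected from time of consent to Day 56; SAEs, MAAEs, and AESIs to be collected from time of consent to EOS".

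**Timing of Dose 2.** Phase 2 SAP, section 7.5.2: "A summary of subjects receiving the dose outside the dosing window, 25 to 31 days post first dose, will be presented". Phase 3 SAP, section 3.8.2, has the same limits. The last Phase 2 contact in the all-event period is listed in Table 2 as "Phone Call - Day 56 (±5d").

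**Counting.** For a repeated event, Phase 2 section 7.7.1 says that "the subject will only be counted once at the preferred terminology level in adverse event frequency tables". A different paragraph of the same section, and section 5.4.1 in Phase 3, says of adverse events in general: "These frequencies will be presented overall and separately by dose".

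**The concern.** A 30-day window needs 30 days of collection behind it. After Dose 2 the plan provides 28. In the days beyond the cut-off, a serious, medically attended or special-interest event can enter the main table, but an ordinary event with the same preferred term cannot. One frequency then combines two ascertainment rules, and the table's title claims a risk period that was only partly observed.

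At stake is the summary that carries the risk differences and will be read as the main safety result. The SAPs also leave open whether Day 56 is a fixed calendar limit, moves with the actual date of Dose 2, or means the date of the phone call. Programmers could therefore treat late events differently from the same data.

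**Working it through.** **Inputs.** Window: 30 days after any dose (sections 7.7.1 and 5.4.1). End of all-event collection: 28 days after Dose 2, given as Day 56 (section 7.7.1; Day 56 alone in both schedule footnotes). Dose 2: Day 28 ± 3 (sections 2.7 and 7.5.2; Phase 3 sections 1.2.4 and 3.8.2). Phase 2 phone call: Day 56 ± 5 (Table 2). First dose is Day 0, and days after a dose are counted as differences in dates.

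**The plan's own figures reproduce.** 28 + 28 = Day 56. 28 − 3 = 25 and 28 + 3 = 31.

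**Gap.** For Dose 2 on Day *d*, the window ends on Day *d* + 30. With collection ending on Day *c*, the gap is max(0, *d* + 30 − *c*).

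| Dose 2 on Day | Window ends on Day | Gap if *c* = *d* + 28 | Gap if *c* = 56, fixed | Gap if *c* = call on Day 51 / 56 / 61 (Phase 2) |
|---|---|---|---|---|
| 25 | 55 | 2 | 0 | 4 / 0 / 0 |
| 28 | 58 | 2 | 2 | 7 / 2 / 0 |
| 31 | 61 | 2 | 5 | 10 / 5 / 0 |

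At nominal timing the gap is 58 − 56 = 2 days. That is 2/30 = 6.7% of the window after Dose 2, and 2/58 = 3.4% of the whole pooled period from Day 0 to Day 58. The largest value, 10/30 = 33.3%, needs the latest permitted Dose 2 and the earliest permitted call together.

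**Does overlap of the two dose windows matter in this table?** The Dose 1 window is Days 0 to 30. The Dose 2 window is Days *d* to *d* + 30. For *d* from 25 to 31 there is no uncovered day between them (at the latest, Day 31 follows Day 30), so their union is one period, Day 0 to Day *d* + 30. The main summary pools events after any dose and counts a subject once per preferred term. An event in both windows is therefore counted once, and overlap changes nothing there.

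**Would changing 30 to 28 after each dose be enough?** No. With Dose 2 on Day 31, separate 28-day windows are Days 0 to 28 and Days 31 to 59. Days 29 and 30 would drop out although all events are collected then. The main summary has to be one continuous period.

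**The case against.** The strongest reply is that very little is lost. About 28 of the 30 days are fully observed. In the remainder, serious, medically attended and special-interest events are still collected, so only other events starting about 29 to 30 days after Dose 2 are missed. The rule is the same in every arm, the 7-day summary lies well inside collection, and an all-time summary exists. All of this stands, and it limits the weight of the point. It does not reconcile a 30-day window with a 28-day collection period set in the same section.

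A reader might also infer two stronger things.

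- **That early Dose 2 reactions are counted twice, or under Dose 1, in the main table.** The calendar windows do overlap: 30 − *d* + 1 gives 6 days for Dose 2 on Day 25, 3 on Day 28 and none on Day 31. But the main summary assigns no event to a dose. The by-dose presentation is in another paragraph that sets no 30-day definition, and in Phase 2 it could mean dose level. Phase 3 has one active dose level, so there it more naturally means dose number. What remains is an unstated assignment rule, not a stated double count.
- **That the window is fully observed only when Dose 2 falls on Day 25 or 26.** This assumes a hard stop on calendar Day 56. If the Phase 2 wording runs from the actual Dose 2, the gap is 2 days for everyone; if it runs to the call, the gap depends on the date of the call.

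**Conclusion.** The point holds in both SAPs as an inconsistency between the main analysis window and adverse-event collection. At nominal timing, 2 of the 30 days after Dose 2 are not observed for ordinary events. The range is 2 days throughout, 0 to 5 days, or (Phase 2) 0 to 10 days, depending on which of three cut-off readings is meant. All three assume Dose 2 within Days 25 to 31.

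The consequence is a mislabelled risk period with mixed ascertainment in its last days. A material bias in the risk differences is not shown and is unlikely, given that all arms share the rule. The documents do not support double counting in the main table. The correction is worth making because it concerns the main safety summary and costs almost nothing.

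**What to change.** In Phase 2 section 7.7.1 and Phase 3 section 5.4.1:

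1. Define the main summary as events with onset from the first dose to the earlier of (a) 28 days after the last dose due (Dose 2, where given) and (b) the end of all-event collection. Treat this as one continuous period, so that no collected day between doses is dropped. State the end date for a subject who never receives Dose 2.
2. State whether the collection cut-off is a fixed Day 56 or 28 days after the actual Dose 2, and label the table to match. Under a fixed Day 56, Dose 2 on Day 31 leaves 56 − 31 = 25 days, and the label should not promise more.
3. Leave later serious, medically attended and special-interest events in the all-time summary, and keep the 7-day summary.
4. In any table by dose number, assign each event to the most recent dose before onset.

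**Cost.** Wording in two sections and minor programming. A few serious, medically attended or special-interest events from the last days leave the main table but stay in the all-time table. If Day 56 is fixed and Dose 2 was early, a little fully collected time leaves as well: with Dose 2 on Day 25 the period ends on Day 53 instead of Day 55. If outputs already exist, the change can be reported in the clinical study report, where both SAPs require deviations to be described and justified.

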### 7.7.2 Clinical laboratory evaluations

For the purposes of summarization in both the tables and listings, all laboratory values will be presented in the International System of Units (SI). If a lab value is reported using a nonnumeric qualifier (e.g., less than (<) a certain value, or greater than (>) a certain value), the given numeric value will be used in the summary statistics, ignoring the nonnumeric qualifier.

All laboratory data obtained after the start of study medication dosing up to and including the final visit will be used for the laboratory safety analysis. Laboratory summaries will be provided including values measured during the follow-up period, where appropriate.

Visit value and change and/or percent change from baseline (where applicable) will be summarized by treatment group using descriptive statistics for all laboratory parameters which are listed in the protocol.

Shift tables among the safety population will be summarized by treatment group using the baseline values and highest/lowest values obtained post baseline. Lab results will be classified as Normal or Abnormal based upon local laboratory normal ranges.

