## Statistical Analysis Plan (SAP) - Phase 2 Segment

- a. Screening assessment occurs from -30 days to -1 day of Day 0.
- b. Full physical examination only at Screening and Day 393 (or EOS). Targeted physical exam at other indicated visits.
- c. Hemoglobin A1c collected at screening only. Chemistry includes Na, K, Cl, HCO3, Ca, PO4, glucose, BUN, Cr, alkaline phosphatase, AST, ALT, LDH, total bilirubin.
- d. Dipstick for glucose, protein, and hematuria. Microscopic examination should be performed if dipstick is abnormal.
- e. Serum pregnancy test at Screening. Urine pregnancy test at other visits.
- f. Intradermal injection(s) in skin preferably over deltoid muscle, or alternately over anterolateral quadriceps muscle, followed by EP at Day 0 and Day 28.
- g. Following administration of INO-4800 or placebo, EP data will be downloaded from the CELLECTRA® 2000 device and provided to Inovio.
- h. AEs to be collected from time of consent to Day 56; SAEs, MAAEs, and AESIs to be collected from time of consent to EOS.
- i. On Day 0, cellular sampling requires 64 mL of whole blood (8 Cell Preparation Tubes (CPT), each 8 mL of whole blood) prior to 1st dose. At all other time points, collect 32 mL of whole blood (4 CPT tubes, each 8 mL of whole blood).
- j. On Day 0, humoral sampling requires a total of 17 mL of whole blood (two 10-mL red top serum collection tubes, each 8.5 mL of whole blood, to produce eight serum aliquots of 1 mL each). At all other time points, collect 8.5 mL of whole blood in a single 10-mL red top serum collection tube to produce four serum aliquots of 1 mL each.
- k. SARS-CoV-2 antibody.
- l. Saliva specimen at Screening; Nasal swab and saliva specimens at COVID-19 assessment and convalescent visits. Genotyping may also be performed on sample(s) collected at the COVID-19 assessment visit.
- m. Subjects will be evaluated during a "COVID-19 assessment visit" when acute COVID-19 is suspected. The assessment visit may be performed in the clinic, in the subject's vehicle or at the subject's home and should be completed within 3 days of symptom onset or within 3 days of a positive result of a SARS-CoV-2 test.

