## 7 Statistical Methods

### 7.1 General statistical conventions

All statistical procedures will be completed using SAS version 9.4 or higher.

Unless otherwise stated, all statistical testing will be two-sided and will be performed using a significance (alpha) of 0.05. Two-sided 95% confidence intervals (CI) will be provided when relevant.

Continuous variables will be summarized using descriptive statistics, including number of subjects (n), mean, median, standard deviation (SD), minimum, and maximum. Means and medians will be rounded to one more

decimal place than what is reported in the data. Standard deviations will be rounded to two more decimal places than what is reported in the data.

For categorical variables, summaries will include counts of subjects and percentages. Percentages will be rounded to one decimal place.

For summary purposes, baseline is defined as the last measurement prior to the first treatment administration. All summaries will be presented by treatment group, unless otherwise specified.

All subject data, including those derived, will be presented in individual subject data listings. Unless otherwise stated, unscheduled visit results will be included in date/time chronological order, within patient listings. All listings will be sorted by investigational site, subject ID, date/time and visit. The treatment group as well as the patient's sex and age will be stated on each listing. Unless otherwise stated, data listings will be based on all subjects randomized (ITT Population).

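### Phase 2 laboratory shift tables with only Normal and Abnormal classes cannot show worsening from an abnormal baseline and do not reliably show direction

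*SAP*

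**What the plan says.** Section 7.7.2 of the Phase 2 SAP plans two kinds of laboratory table.

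- **Shift tables.** "Shift tables among the safety population will be summarized by treatment group using the baseline values and highest/lowest values obtained post baseline". The classification rule is the next sentence: "Lab results will be classified as Normal or Abnormal based upon local laboratory normal ranges". There is no split into low and high and no laboratory grade. The section does not say whether highest and lowest are tabulated separately or reduced to one worst value.
- **Numeric summaries.** "Visit value and change and/or percent change from baseline (where applicable) will be summarized by treatment group using descriptive statistics". Under section 7.1, descriptive statistics means "including number of subjects (n), mean, median, standard deviation (SD), minimum, and maximum".

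Section 7.1 also provides that "All subject data, including those derived, will be presented in individual subject data listings", and for summary purposes "baseline is defined as the last measurement prior to the first treatment administration". The chemistry panel is in note c to Table 2 and includes "glucose, BUN, Cr, alkaline phosphatase, AST, ALT, LDH, total bilirubin". Complete blood count and urinalysis are collected as well. Section 1 leaves table templates to a separate document.

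**The concern.** Taking both the highest and the lowest post-baseline value is a directional step: the first looks for rises, the second for falls. The classification that follows has no direction and no size, so part of what was selected is discarded when the table is filled.

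Safety and tolerability are the secondary objective of the segment. The shift table is the only planned laboratory table that relates values to the normal range and counts subjects by category. If it cannot show that a subject with an already raised liver enzyme became much worse, or that a blood count or potassium moved from one side of its range to the other, a comparison between arms on those events has to be pieced together from other outputs.

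**Working it through.** The SAP states no figure on this point, so there is none to reproduce. The check is an enumeration of what the table can distinguish.

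**Inputs.** The two-level classification, and the use of baseline, lowest and highest post-baseline values (both section 7.7.2). Write each value as L (low), N (normal) or H (high), in the order baseline, lowest, highest.

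**Number of patterns.** There are 3 baseline classes and 6 pairs with lowest not above highest (LL, LN, LH, NN, NH, HH), so 3 × 6 = 18 patterns. Of these, 2 × 6 = 12 have an abnormal baseline and 6 a normal one. These are counts of possible patterns, not frequencies of subjects.

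**Step 1: abnormal baseline.** The only cells are Abnormal to Abnormal and Abnormal to Normal.

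- Highest-value table: Abnormal to Abnormal holds 8 of the 12 patterns (LLL, LLH, LNH, LHH, HLL, HLH, HNH, HHH). A persistent low, a persistent high and a move from low to high are indistinguishable. The other 4 (LLN, LNN, HLN, HNN) read as improvement, including HLN, where a high baseline was followed by a low value.
- Lowest-value table: again 8 and 4.
- Merged into one worst value: Abnormal to Abnormal holds 10 of the 12.

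In no layout does a cell mean worse than baseline.

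**Step 2: normal baseline, separate tables.**

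- Highest-value table: Normal to Abnormal holds 4 patterns (NLL, NLH, NNH, NHH). Three contain a high value; NLL is the exception, where every post-baseline value is low.
- Lowest-value table: Normal to Abnormal holds NLL, NLN, NLH and NHH. Three contain a low value; NHH is the exception.
- Read jointly for the same subject, lowest normal with highest abnormal can only be a rise (NNH), and lowest abnormal with highest normal can only be a fall (NLN). Both abnormal is ambiguous among 3 patterns (NLL, NLH, NHH).

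Direction is therefore largely, but not fully, recoverable. The joint reading also needs the two results linked within subject, which two separate tables of counts do not supply.

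**Step 3: normal baseline, merged table.** Normal to Abnormal holds 5 of the 6 patterns (NLL, NLN, NLH, NNH, NHH). Falls and rises share the cell and direction is lost.

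**Step 4: size.** As an illustration, an ALT 1% above its limit is at 1.01 times the limit. A tenfold rise takes it to 10 × 1.01 = 10.1 times the limit. Both are Abnormal, so the table shows no shift. From a normal baseline, final values of 1.01 and 10.1 times the limit fall in the same cell.

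**Step 5: effect of adding Low and High.** Each table becomes 3 × 3. Low to High and High to Low then have their own cells, and the highest-value and lowest-value tables each carry an explicit direction. High to much higher still sits in High to High, so the example in step 4 needs a count based on size as well.

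**The case against.** The strongest reply is that the shift table does not stand alone, and three parts of it hold.

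- A reader might infer that the shift table is the only planned view of individual laboratory change. It is not. Section 7.1 plans listings of all subject data, which show the size and course of every value.
- The numeric summaries include minimum and maximum. A tenfold ALT rise that a mean would dilute would still tend to show in the arm's maximum value, and in its maximum change where change is tabulated.
- A reader might also infer that a fall can never be told from a rise. Step 2 shows this is too strong: with separate tables, most patterns from a normal baseline keep their direction. The templates, which are not shown, may specify that layout.

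What remains is narrower. A minimum and a maximum give one extreme per arm and visit. They do not say how many subjects had an excursion or whether it started from an abnormal baseline. If local ranges differ between sites, a pooled maximum cannot be read against a limit. Listings allow these facts to be reconstructed but do not count them. Adverse event tables contain a laboratory change only if it was reported as an event.

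It could be added that treatment-labelled listings could not serve dose selection while subject-level blinding was kept. That adds little here: section 7.8 describes data collection for that step as complete, and the Phase 3 SAP already carries a single dose level.

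**Conclusion.** The point holds as a minor weakness in reporting. Within the Phase 2 shift tables, worsening from an abnormal baseline cannot be displayed, whatever the layout. Direction is not reliable with separate tables and is lost if highest and lowest are merged. Size is never shown. No other planned laboratory table counts subjects per arm by direction or size of excursion.

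Laboratory shifts are not among the endpoints in section 3, section 4 states that the segment is not powered for formal testing, and no estimate, test or sample size changes.

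The number of subjects affected cannot be derived from the SAP, which gives no laboratory rates. A reader might be tempted by a calculation over the 14 chemistry analytes in note c. If 5% were abnormal per analyte and analytes were independent, 1 − 0.95^14 = 51% of subjects would have at least one abnormal baseline value. At 2.5% the result is 30%, and at 1% it is 13%. These figures do not measure the harm. The rates are assumed, and several analytes are physiologically linked (AST with ALT, BUN with creatinine). The result also counts abnormal baselines, whereas hidden worsening further requires deterioration after dosing.

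**What to change.** In section 7.7.2 of the Phase 2 SAP:

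1. Classify each result as Low, Normal or High against the local range.
2. State that baseline versus highest and baseline versus lowest post-baseline value are separate shift tables, each by treatment group.
3. Add, per arm and analyte, the number of subjects whose worst post-baseline value exceeds prespecified multiples of the local limit or of their own baseline, with the corresponding fractions for falls. Severity grades may be used instead where the protocol supplies them for that analyte. The Phase 2 SAP names no laboratory grading scale, so the plan should not rely on one without a reference.

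Items 1 and 2 restore direction. Item 3 is needed for worsening in the same direction, which the three-level table still leaves in one cell.

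The cost is a change of SAP wording, table programming on values and local ranges already needed for the planned tables, and a few more table pages.
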